1.1 Background

Hepatitis D is caused by a defective RNA-virus, that is known to be among the smallest human pathogenic viruses. As it partly shares the viral entry into hepatocytes with HBV, a coinfection is mandatory (1). Besides a simultaneous infection with HBV and HDV, it might also occur in the sense of a superinfection to a preexisting HBV-infection (2). Though most of the acute infections recover spontaneously, a progression to chronic disease is well described (3). The persistence of HDV leads to an accelerated fibrosis progression and eventually to cirrhosis and an increased risk of developing hepatocellular carcinoma (HCC) as well (4, 5). With the widely established feasibility of immunization against viral Hepatitis B, numbers of HDV-infection in high-income countries are quite low. Nevertheless, the burden of chronic HDV-infection worldwide is high, as different studies estimate the number of patients from 12 million to up to 72 million (6-8).

In the subgroup of people living with HIV (PLWH), who are at increased risk for acquiring viral hepatitis in general, rates of HDV infection have been reported between 10%-20% of HIV/HBV-coinfected people, with variations according to region as well as transmission group. Particularly, early in the HV epidemic higher rates of HDV have been reported for HIV/HBV coinfected drug users. More recently, a shift from people who acquired HIV through drug injection (PWID) to men who have sex with men (MSM) has been reported with HDV coinfection rates of around 8% (9). Common for all PLWH with HBV/HDV-coinfection is a more rapid progression in liver disease (10), resulting in increased rates of decompensated cirrhosis and higher mortality (11, 12). Therefore, mandatory screening for HDV was implemented into current EACS guideline recommendations. However, there is still a lack of testing in daily routine, even at sites where testing is easily accessible and reimbursed. Moreover, most PLWH

who are coinfecte with HBV are tested at initial HBV diagnosis, but after being put on antiretroviral treatment, which usually includes a tenofovir-based therapy a follow-up testing of HDV does not take place routinely.

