2.2 Study Centers and Accrual of Patients

To secure representative data, each cohort or clinic network will aim to enroll a sample size of at least 20% of all HIV/HBV-coinfected individuals in each country. France, Switzerland, Italy, and The Netherlands already have well established national cohorts which are representing more than 50% of all PLWH in their respective countries. In the remaining countries (Germany, Spain, Poland, Portugal, UK) well-defined cohorts in specialized HIV-clinics or networks of HIV-centers are existing, which allow for a sufficient recruitment. The overall number of participants is planned to reach at least 8000 HIV/HBV-coinfected persons. With an estimated 800.000 PLWH in the following 9 countries: Spain 150.00, France 190.000, Germany 93.000, England 106.000, Portugal 61.000, Italy 140.000, Poland 20.000, Switzerland 16.000, Netherlands 24.000, and an estimated HBV-Prevalence of 5%, this would lead to a cohort of around 40.000 HIV/HBV coinfecte individuals. According to current data, 20% of HIV/HBV-coinfected PLWH are expected to have an HDV-infection, which should add up to 8000 individuals that would be needed to be studied. This should guarantee a representative sample size and would represent a highly meaningful European cohort for future HDV studies.

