2.3 Accrual goal

A cohort of 8000 HIV/HBV-coinfected individuals with serological HDV-screening evidence.

3. Patient Inclusion and Exclusion Criteria

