5.2 Define burden of disease

- Assess the rate of HDV-positive patients with ongoing HDV replication
- Define the liver disease stage by non-invasive methods (APRI, Fibroscan)

Methods:

- HDV-replication will be measured by commercially used PCR-testing kits. The proportion of HDV serological positive individuals with ongoing viral replication will be determined. This will be collected for all patients with positive HDV serology.
- The liver disease stage, which is expressed by the fibrosis stage, will be determined by APRI score. Furthermore, other non-invasive imaging techniques, including standard ultrasound as well as Fibroscan will be used where available to evaluate the degree of liver disease. In addition, standard laboratory parameters (see, eCRF codebook, annex xyz), which are part of the routine testing among PLWH control visits, will be documented. Changes over time will be evaluated and put in relation to medical imaging, as far as available.

6. Study withdrawals

Patients will be free to withdraw their consent at any time and without any reason. Withdrawal of consent will not affect the rights of the patient or their access to continuing medical care or treatment.

7. Ethics and research governance

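### Protocol 2.2 derives the 8000 target as a count of HDV-infected persons, but the target is 8000 HIV/HBV-coinfected persons, who would be expected to include about 800 to 1600 HDV-positives

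*Protocol*

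**What the plan says.** Section 2.2 gives the target as follows: "The overall number of participants is planned to reach at least 8000 HIV/HBV-coinfected persons". Section 2.3 repeats the unit and adds a condition: "A cohort of 8000 HIV/HBV-coinfected individuals with serological HDV-screening evidence".

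The derivation, also in 2.2, has three steps:

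- It starts from the source population: "With an estimated 800.000 PLWH in the following 9 countries".
- It then applies "an estimated HBV-Prevalence of 5%, this would lead to a cohort of around 40.000 HIV/HBV coinfecte individuals".
- It ends with the statement that "20% of HIV/HBV-coinfected PLWH are expected to have an HDV-infection, which should add up to 8000 individuals that would be needed to be studied".

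The protocol then says that this should give a representative sample size and a cohort of value for future HDV research.

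Earlier in 2.2 a different 20% appears, as a sampling fraction: each cohort or network is to enrol "a sample size of at least 20% of all HIV/HBV-coinfected individuals in each country". Section 1.1 gives a range for HDV prevalence: "rates of HDV infection have been reported between 10%-20% of HIV/HBV-coinfected people". Among the aims that rest on HDV-positive persons, section 5.2 states: "The proportion of HDV serological positive individuals with ongoing viral replication will be determined".

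**The concern.** The last step of the derivation multiplies a number of HIV/HBV persons by an HDV prevalence, so its result counts HDV-infected persons. The target counts HIV/HBV persons. The two figures share the value 8000 only because the HDV prevalence and the sampling fraction are both set at 20%, and the text uses the prevalence where the sampling fraction belongs.

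A reader could conclude that about 8000 HDV-infected persons will be studied. The replication rate, the liver disease stage of HDV-positive persons and the cohort for future HDV studies depend chiefly on how many HDV-positives are found, and the protocol nowhere states that number correctly. The planning prevalence is also the top of the protocol's own range, so even a correctly placed calculation at 20% would give the most favourable figure in that range. The testing-rate and prevalence aims rest on HIV/HBV persons and are not affected.

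**Working it through.** **Inputs**

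- Country figures for people living with HIV (2.2), in thousands: Spain 150, France 190, Germany 93, England 106, Portugal 61, Italy 140, Poland 20, Switzerland 16, Netherlands 24. Spain is printed as 150.00 and is read here as 150,000, the value that makes the list agree with the stated total.
- HBV prevalence: 5% (2.2).
- HDV prevalence among HIV/HBV persons: 20% (2.2); range 10% to 20% (1.1). Section 1.1 also mentions around 8% in connection with men who have sex with men.
- Sampling fraction: at least 20% of HIV/HBV persons per country (2.2).

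**Reproducing the protocol's figure**

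- 150 + 190 + 93 + 106 + 61 + 140 + 20 + 16 + 24 = 800, that is 800,000 persons.
- 800,000 x 0.05 = 40,000 HIV/HBV persons.
- 40,000 x 0.20 (HDV prevalence) = 8000 **HDV-infected** persons in all nine countries.

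The arithmetic reproduces exactly, but the unit of the result is not that of the target.

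**The same number in the right unit**

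- 40,000 x 0.20 (sampling fraction) = 8000 **HIV/HBV** persons to enrol.

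**Expected HDV-positives among 8000 screened HIV/HBV persons**

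| HDV prevalence | Expected HDV-positives | Ratio of 8000 to this number |
|---|---|---|
| 20% | 8000 x 0.20 = 1600 | 5 |
| 10% | 8000 x 0.10 = 800 | 10 |
| 8% (side figure) | 8000 x 0.08 = 640 | 12.5 |

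**What studying 8000 HDV-infected persons would take**

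- At 20%: 8000 / 0.20 = 40,000 HIV/HBV persons, the entire estimated source population.
- At 10%: 8000 / 0.10 = 80,000, twice that population, which would itself hold only 40,000 x 0.10 = 4000 HDV-infected persons.

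**Effect on precision**

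Two assumptions are not in the protocol: a replication proportion of 50% (the value that gives the widest interval) and a PCR result for every HDV-positive person. The 95% half-width is 1.96 x sqrt(0.25 / n):

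- n = 8000: 1.10 percentage points
- n = 1600: 2.45 percentage points
- n = 800: 3.46 percentage points

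**The case against.** The strongest reply is that nothing operational depends on the faulty sentence. The target is stated twice in HIV/HBV persons, section 5 says that no power calculation is made and that the statistics are descriptive, and no analysis uses a count of 8000 HDV-positives. The sampling fraction and the 40,000 stand in the same section, so the correct derivation is one multiplication away. Half-widths of about 2.5 to 3.5 points are adequate for a descriptive proportion, and the protocol sets no precision target that could be missed. All of this stands, and it limits the weight of the point. It does not make the sentence right: the protocol chose to give a justification, and it justifies a different quantity.

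It can also be said that 2.2 opens with the per-country fraction as its route to representative data, so the prevalence sentence is not the only support for that claim. That is fair. Even so, the claims of representativeness and of value for HDV research follow directly after the prevalence calculation, and the second of these depends on the HDV-positive count.

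A third reply is that the sponsor may have wanted 8000 HDV-infected persons. Sections 2.2 and 2.3 both state the target in HIV/HBV persons, and 8000 HDV-infected persons would require the whole estimated source population at 20%, so this reading is hard to sustain.

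Finally, the 800 to 1600 range holds only if all 8000 have an HDV result, and section 1.1 reports gaps in routine testing. Section 2.3 makes screening evidence part of the goal, but the expected yield should be worded as conditional on it.

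**Conclusion.** The point holds. The sample-size reasoning in 2.2 is in the wrong unit, and nothing else in the protocol corrects it. Read as written, it overstates the expected number of HDV-positives in the planned cohort by a factor of 5 at 20% prevalence and 10 at 10%. This rests on the protocol's own prevalence range and on all 8000 participants being screened. The target of 8000 HIV/HBV persons stands, supported by the 20% sampling fraction. The error should be corrected because it concerns the number behind the HDV-positive aims, but it does not call for a redesign.

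**What to change.** In section 2.2:

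1. State that 8000 is a 20% sample of the estimated 40,000 HIV/HBV persons in the nine countries.
2. Delete the sentence that derives 8000 from HDV prevalence.
3. State that 8000 screened persons would be expected to include 800 to 1600 HDV-positives (10% to 20%), and name this as the basis for the replication, liver-stage and future-cohort aims.

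The cost is a change of text and stated figures only. Enrolment, the target and the analysis stay as they are. The stated size of the HDV cohort becomes less favourable.

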2.3 Accrual goal

A cohort of 8000 HIV/HBV-coinfected individuals with serological HDV-screening evidence.

3. Patient Inclusion and Exclusion Criteria

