1.2 Objective

The aim of this project is to set up a cross-sectional cohort study (France, Germany, The Netherlands, Poland, Spain, Switzerland, Italy, United Kingdom and Portugal) to assess the implementation of EACS guidelines for HDV-testing among PLWH with positive HbsAg and thereby evaluate the prevalence of HDV infection among HIV/HBV-coinfected in 2023, as well as corresponding risk factors. In addition to the testing itself, this study will also set up a cohort and database for future HDV studies among PLWH, including clinical, virological und laboratory parameters.

1. Analyze the rate of HDV-testing and evaluate the prevalence of HDV-infection by testing.
 - a. Evaluation of former screening of HDV by assessing existing data at study sites.
 - b. Determination of the HDV prevalence in European PLWH and HBV coinfection.
2. Setting up a database of all PLWH with HBV/HDV coinfection
 - a. Analysis of transmission risk factors for HDV coinfection
 - b. Asses the rate of HDV positive patients with ongoing HDV replication.
 - c. Define the liver disease state by APRI score, fibroscan, ultrasound and routine laboratory test results.

2.Cohort Design and Methods

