2.1 General

In this multi-center cohort study patients with documented HIV/HBV-coinfection (2 measurements of positive HBsAg > 6month interval and Anti-HBc-positive) will be evaluated for past HDV screening (last 24 months).

Eligible participants must be 18 years of age or older.

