3.1 Inclusion-Criteria

Documented HIV-infection with current Hepatitis B infection, who are serological positive for HBSAg

Both, HIV- and HBV Infection must be confirmed by HIV ELISA and HBV HBsAg-testing (2 measurements of positive HBsAg > 6month interval). The viral load results will be included into the analyses, but are not part of the inclusion criteria.

As patients are enrolled retrospectively, data on liver enzymes (transaminases, gamma GT, AP, bilirubin) and viral load will be available, though this is not compulsory. Written informed consent will be provided prior to inclusion, or, if adequate, used from pre-existing cohort studies.

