3.2. Exclusion-Criteria

PLWH with a cleared HBV-infection will be considered as HIV-monoinfected persons. Individuals younger than 18 years of age will be excluded from the analysis.

Patients with any social condition or living circumstances which may interfere with the conduct of the study, as anticipated by the investigator, such as incapacity to adequately understand the study content or not willing to cooperate will be excluded from the study.

For France, patients without adequate social security will be excluded.

4. Study Procedures

All participating PLWH will be recruited from the already existing national cohorts and defined networks of specialized HIV-clinics, respectively. This database will allow for the initial analysis of whether HDV screening was performed and allow to determine the HDV prevalence in the participating countries as well as study risk factors for HDV transmission.

Only patients who were alive in 2022 will be included into the study.

5. Plan of Analysis

Because of the observational nature of the study no predefined statistical power calculations can be made. Descriptive statistics will be used.

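### The Section 5.1 prevalence counts HDV-untested patients as negative, and Section 2.3 ties the accrual goal to an HDV-screening condition that eligibility does not contain

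*Protocol*

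**What the plan says.** Objective 1 in Section 1.2 has two parts. The first is the testing rate: "Evaluation of former screening of HDV by assessing existing data at study sites". The second is to "evaluate the prevalence of HDV-infection by testing". Section 2.1 has coinfected patients assessed for HDV screening over the preceding 24 months, and Section 4 adds: "This database will allow for the initial analysis of whether HDV screening was performed".

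On who is enrolled, Section 3.1 asks for "Documented HIV-infection with current Hepatitis B infection, who are serological positive for HBSAg". Neither 3.1 nor 3.2 sets an HDV-test condition. Milestone 5 in Section 8 likewise counts HBsAg-positive patients who are eligible or reachable.

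On numbers, Section 2.2 states: "The overall number of participants is planned to reach at least 8000 HIV/HBV-coinfected persons". Section 2.3 states the goal as "A cohort of 8000 HIV/HBV-coinfected individuals with serological HDV-screening evidence". Section 2.2 also arrives at 8000 by a different route, as the number expected to have HDV infection, "which should add up to 8000 individuals that would be needed to be studied".

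On analysis, Section 5.1 defines prevalence as the number of HDV-positive persons relative to all coinfected individuals in the database. It neither restricts this to persons with an HDV result nor says how those without one are handled.

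**The concern.** A person with no HDV result cannot be in the numerator of the 5.1 ratio but is always in its denominator. The ratio is therefore a prevalence only if everyone in the database has a result. The protocol gives reason to expect otherwise: Section 1.1 reports a lack of routine testing, and measuring that gap is part of objective 1. The better the study succeeds in enrolling untested patients, the further its prevalence figure falls below the value among the tested. Countries with different testing coverage would also show different prevalences even if infection were equally common.

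The wording of 2.3 adds a second problem. It attaches to the accrual goal a condition that is itself an outcome of objective 1. A site could take it as a guide to whom to enter.

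**Working it through.** **The plan's own figure.** The country counts in 2.2 sum to 800,000 if the Spanish figure, printed with a digit missing, is read as 150,000. Then 800,000 × 5% = 40,000 coinfected, and 40,000 × 20% = 8,000. The arithmetic reproduces. The 20% here is the expected HDV rate, so this 8,000 counts HDV-infected persons. The same number follows from the sampling floor in 2.2, 20% of 40,000 coinfected, and there it counts persons to enrol. With 8,000 enrolled and the 10% to 20% HDV rate of Section 1.1, one would expect 800 to 1,600 HDV-positive persons if all were tested.

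**The 5.1 ratio.** Let t be the share of the database with an HDV result and p the prevalence among them. The 5.1 ratio is then t × p. The values of p are the 10% and 20% of Section 1.1. The values of t are assumptions, because the protocol gives none. The last column is 1.96 × √(0.1 × 0.9 / n), with n the number having a result.

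| Assumed t | With a result among 8,000 | p = 10% reads | p = 20% reads | 95% half-width for tested-only prevalence at 10% (points) |
|---|---|---|---|---|
| 30% | 2,400 | 3% | 6% | 1.20 |
| 50% | 4,000 | 5% | 10% | 0.93 |
| 70% | 5,600 | 7% | 14% | 0.79 |
| 90% | 7,200 | 9% | 18% | 0.69 |

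With all 8,000 tested the half-width would be 0.66 points.

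**Selective testing.** Let u be the prevalence in the untested. The true value is t × p + (1 − t) × u. The 5.1 ratio is too low by (1 − t) × u. Prevalence among the tested only is too high by (1 − t) × (p − u) when u is below p. The two errors are equal at u = p/2. Above that the tested-only figure is closer; below it the 5.1 ratio is closer. Example at the tie, with p = 10% and an assumed u = 5%: at t = 50% the true value is 7.5%, 5.1 reads 5% and tested-only reads 10%, each 2.5 points off. At t = 70% and 90% each is 1.5 and 0.5 points off.

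**Is untested status resolved within the study?** The passages point both ways.
- For in-study testing: Section 1.2 speaks of evaluating prevalence through testing and presents testing as a study component alongside the cohort and database.
- Against: Section 4 has no serology step, Section 7.1 calls the study retrospective, and Section 9 says the data used have already been collected. The PCR measurement in 5.2 concerns patients whose HDV serology is already positive.

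**If 2.3 were used as a selection rule.** Every enrolled person would have been tested, so the ever-tested rate would be 100% by construction. If screening evidence means a test at any time, the 24-month rate of 2.1 would be inflated by 1/t: 2.0-fold at t = 50% and 1.1-fold at t = 90%.

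**The case against.** The strongest reply is that testing is part of the study. On that reading 2.3 describes the cohort after testing, everyone has a result, and both problems disappear. Section 1.2 lends this real support. It does not settle the matter, because no procedure for testing unscreened patients is given and Sections 7.1 and 9 describe existing data. What stands is that this is an ambiguity to resolve, not a proven bias.

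A reader might infer more from 2.3: that never-tested patients will be kept out, that the testing rate will be inflated, and that no analysis could recover those left out. The protocol does not support this. Section 2.3 is a goal and not an eligibility rule, Sections 2.1 and 4 presuppose untested patients in the database, and no text tells sites to exclude them. Patients come from existing cohorts and clinic networks, so untested HBsAg-positive patients would plausibly remain identifiable. Nor are the 2.2 and 2.3 targets incompatible: 2.2 sets a minimum, and a larger cohort could meet both. Screening evidence might also mean only that screening status is on record. That would ease the conflict over 2.3 but leave the 5.1 denominator untouched.

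It can also be said that prevalence among the tested is no safe substitute, since testing may have been directed at those at higher risk. That is correct, and it is why both figures should be reported.

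**Conclusion.** The point holds for 5.1 as written. If patients are enrolled by Section 3 and some stay untested, the defined ratio understates prevalence whenever any of the untested are infected. The direction does not depend on the coverage assumed. The size does: 10% would read 3% to 9%, and 20% would read 6% to 18%, under an assumed coverage of 30% to 90%. Section 1.1 says that most are tested at HBV diagnosis, but this is too loose to serve as a floor of 50%.

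The mismatch between 2.3 and 2.2, 3.1/3.2 and milestone 5 is certain as a matter of wording. Inflation of the testing rate is only a conditional risk, should sites read 2.3 as a selection rule.

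This is not a matter left to the statistical analysis plan. The protocol itself fixes the accrual goal and the prevalence denominator, and a plan that used another denominator would contradict 5.1.

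**What to change.** 1. State whether unscreened patients are to be HDV-tested within the study. If so, add the step to Section 4 and reconcile Sections 7.1 and 9.
2. Restate 2.3 as at least 8000 eligible HBsAg-positive people living with HIV, enrolled irrespective of prior HDV testing.
3. Use all enrolled patients as the denominator of the testing rate, with the 24-month window of 2.1.
4. In 5.1, report prevalence among those with an HDV result, together with the number untested and a comparison of tested and untested patients. Keep the present all-enrolled ratio beside it, labelled as a lower bound.
5. As a side point, reconcile the two meanings of 8000 in 2.2: persons to enrol, and persons expected to have HDV infection.

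The cost is a few sentences in 2.2, 2.3 and 5.1 and an instruction to sites. No new data collection is needed unless in-study testing is chosen. There are two downsides. Intervals widen somewhat (see the table above). The tested-only figure is biased upward if testing was risk-targeted, and this should be named as a limitation.
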